- CBC, platelets, creatinine, AST, ALT, and bilirubin will be monitored bi-weekly during administration (weeks 2, 4, and 6).
- Blood for immune research studies* (10 to 40 cc) may be collected in week 2-3 after the NSC-CRAd injection and 2-4 weeks after completion of radiation therapy
- MRI of the brain approximately 28 days after study product injection, 2-4 weeks after completion of radiation, and then every 2-3 months for the first year or until disease progression.
- If surgery is performed, tumor samples will be examined in conjunction with the pathologist and samples retained for future studies if consent given by the patient.
- Evaluation once a year for 5 years. Evaluations will include: Physical and neurological examination, MRI, and CBC with differential count.

Statistical Considerations:

Statistical analysis will be descriptive only, with no hypothesis testing. All the endpoint data will be collected and described in summary tables for both two arms at each dose. In general, descriptive statistics (n, mean, standard deviation, median, minimum, and maximum) will be presented for continuous variables. Frequencies and percentages will be calculated for categorical and ordinal variables at each category. All study data will be presented in by-subject data listings. Statistical analyses will be performed using SAS9.4 (SAS Institute Inc., Cary, NC).

The maximum tolerated dose (MTD) will be determined according to the dose escalation algorithm. If >2 patients do not complete the initial RT/TMZ phase or rule if > 2 patients experience life threatening or fatal neurologic toxicity, the trial will be stopped to analyze, in conjunction with the DMC, whether this regimen is tolerable.

Demographic (age, sex, height and weight) and baseline disease characteristics (including baseline KPS), will be summarized for both arms as well as the entire group. Kaplan-Meier curves and median survival estimates with confidence limits will be given for both overall survival and progression-free survival. The association of extent of immune response with overall survival will be determined by Cox's proportional hazards model.

Safety parameters will be analyzed descriptively, and presented in standard frequency tables (adverse events), shift tables (Laboratory parameters) and summaries of change from baseline over time (vital signs, physical examination, ECG and laboratory parameters).

Sponsor/Licensee:

Northwestern University/[name]

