5.0 STUDY PROCEDURES

All patients will undergo all standard of care and clinically indicated evaluations in addition to any study specific evaluations. **Table 3** presents a summary sample schedule. **Table 4** outlines the treatment evaluation schedule. **Table 5** presents the entire study calendar.

Table 3– Sample Schedule	
Screening	
Day -28 until Day -1	Informed consent, medical history and physical exam. baseline laboratory assessments, MRI
Week 1	
Day 0	Intratumoral injection of NSC-CRAd-S-pk7
Days 6-7 (+ 3days)	Simulation for RT
Week 2-7	
Days 1-7 (+ 3days)	RT (1.8-2 Gy) (Days 1-5 only) TMZ (75 mg/m ²)
Week 12	
5 Days on/23 Days off	TMZ (150-200mg/m ²)

Table 4 – Treatment Evaluation Schedule	
History, Physical Exam	≤ 7 Days from Day 0 Weekly 2-4 weeks after completion of XRT At least every three months for first year Annually for five years
Quality of Life questionnaire (FACT-Br version 4) and mini-mental status exam	≤ 7 Days from Day 0 Once during RT administration (week 2 or 3) 2-4 weeks after completion of RT Every three months for the first year or until disease progression
CBC, platelets, PT, PTT, serum electrolytes, creatinine, liver function tests-AST, ALT and bilirubin	≤ 7 Days from Day 0 Weekly during administration (weeks 2, 4, and 6) Annually for five years (CBC Count)
Blood collection for immune research studies*	≤ 7 Days from Day 0 (may be collected in week 2-3 after the NSC-CRAd injection and 2-4 weeks after completion of RT)
Blood collection for RCR testing*	≤ 7 Days from Day 0, 3 months, 6 month, and one year, then annually
Urine/serum pregnancy test (if applicable)	≤ 7 Days from Day 0
Brain MRI	≤ 21 Days from Day 0 2-4 weeks after completion of RT

	Every two-three months for the first year or until disease progression Annually for five years
--	---

Table 5. Activities	Screening	Study Drug Administration Period							Follow-up Period			
	Day -28 to -1	Day 0	Day 1	Day 2	Day 3	Day 7	Day 14	Day 28	Day 42	Day 56, every 8 weeks thereafter	Yearly	
Clinical Assessments												
Informed Consent	X											
Medical/Cancer History	X											
Physical Exam /targeted neurological exam	X	X	X	X	X	X	X	X		X		X
KPS	X	X						X	X		X	X
Height (only at Screen) and Weight	X					X	X	X				
Vital Signs	X	X	X	X	X	X	X	X				
Adverse Events	X	X	X	X	X	X	X	X		X		
Concomitant Meds	X	X	X	X	X	X	X	X			X	
Quality of Life Measures	X						X				X ³	
Clinical Laboratory												
Urine or serum Pregnancy test	X	X										

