6.2 Secondary Endpoints

This phase 1 study is not powered to detect statistically significant differences in efficacy.

However, data will be collected and described descriptively on the following endpoints:

- objective tumor response: objective response to therapy as determined by iRANO criteria (table 9)
- overall survival : time from study project injection to death
- progression-free survival : time from study project injection to first confirmed disease progression as determined by objective tumor response
- quality of life: summary score on patient self-report measure, Functional Assessment of Cancer Therapy- Brain component (as determined by patient self-report on FACT-Br v4, appendix C)

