6.3 Exploratory Endpoints

Correlation of cytokine profile and blood immune response with overall survival. Correlation of RCR testing with overall survival.

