9.0 CORRELATIVES/SPECIAL STUDIES

An exploratory objective will be to evaluate serum cytokine profile and blood immune response to NSC-CRAd-S-pk7 and to determine whether overall survival rate correlates with extent of immune response. In addition, replication competent retrovirus (RCR) testing will be performed by analyzing patient DNA from whole blood for RCR-specific sequences at baseline, 3 months, 6 months, and 1 year after study treatment; and annually thereafter, and to determine whether overall survival rate correlates with persistent gene expression. Real time PCR with 4070A envelope-specific primers will be used to screen DNA extracted from PBMCs from study patients treated with NSCs.

Correlative study (sample type)	Cytokine profile (serum)	Immune response (whole blood)	RCR testing
Mandatory or Optional	Mandatory	Mandatory	Mandatory
Timing (+/- windows)	Baseline, Days 1, 3, 7, 14 and 28 after	Baseline, Days 1, 7, 14 and 28 after study	Baseline, 3 months, 6 months, and 1 year

	study product injection	product injection	after study product injection
Volume Needed (blood only)	4-5 ml	4-5 ml	4-5 ml
Tube type needed (blood only)	EDTA tube	Non-EDTA tube	Non-EDTA tube
Tissue thickness and/or # slides (tissue only)	NA	NA	NA
Processing center	Lurie Research Center (LRC) 3-250	Lurie Research Center (LRC) 3-250	Lurie Research Center (LRC) 3-250
Sample handling/processing instructions	Blood transported directly to LRC within 30 minutes of draw; centrifuge 15 minutes at 3000 rpm; pipette serum into vial and freeze at -80°C until analysis	Blood transported directly to LRC within 30 minutes of draw; freeze at -80°C until analysis	Blood transported directly to LRC within 30 minutes of draw; freeze at -80°C until analysis
Shipping/delivery info	NA	NA	Samples shipped to City of Hope for analysis
Storage needs	Storage available in LRC	Storage available in LRC	Storage available in LRC
Analysis center	LRC	LRC	LRC
Assay methodology	ELISA	ELISA	Real time PCR with 4070A envelope-specific primers

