10.3.2.3 Analysis of the Secondary Endpoint(S)

For objective tumor response, a summary table will be produced to present the number and proportion of responders in each arm, together with each of the response categories, namely CR, PR, MR, SD, P and PP.

The analysis of overall survival and progression-free survival are based on the survival function, estimated by the Kaplan-Meier method. Survival will be calculated from the day of study inclusion until progression and death, respectively, or will be censored at the date of last available follow-up information. The survival function will be summarized for 25th percentile, median, and 75th percentile, and the survival curves of the two arms will be presented.

Descriptive statistics will be used to describe the overall quality-of-life score on physical well-being, social/family well-being, emotional well-being, functional well-being and additional concerns, respectively.

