10.3.2.4 Analysis of the Exploratory Endpoint(S)

Cytokine profile will be described using descriptive statistics, and blood immune response to NSC-CRAd-S-pk7 will be presented as number (percentage) for each category. The association of extent of immune response with overall survival will be determined by Cox's proportional hazards model.

In addition, retroviral testing (RCR testing) will be performed by analyzing patient DNA from whole blood for RCR-specific sequences prior to surgery; at 3 months, 6 months, and 1 year after study treatment; and annually thereafter.

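### Markers measured after injection are related to survival counted from injection or earlier, with no landmark, time-dependent term or rule for early deaths; the risk is large for RCR and small for immune response

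*Combined protocol and SAP*

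**What the plan says.** **Analyses.** For immune response, Section 10.3.2.4 states "The association of extent of immune response with overall survival will be determined by Cox's proportional hazards model". It does not say which sample or summary defines the extent of response. For RCR, Section 6.3 lists "Correlation of RCR testing with overall survival" as an exploratory endpoint, and Section 9.0 gives the aim "to determine whether overall survival rate correlates with persistent gene expression". The Study Summary makes this correlation conditional on expression being found. No model or coding is given for RCR.

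**Sampling.** For immune response, the Section 9.0 table (mandatory samples) gives "Baseline, Days 1, 7, 14 and 28 after study" product injection. The Study Summary and Table 4 differ: Table 4 says blood "may be collected in week 2-3 after the NSC-CRAd injection and 2-4 weeks after completion of RT". RCR is tested before treatment, at 3, 6 and 12 months, and then annually.

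**Survival clock.** Section 6.2 has "overall survival : time from study project injection to death". Section 10.3.2.3 has "Survival will be calculated from the day of study inclusion until progression and death, respectively". Both origins precede every post-injection sample.

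**Analysis set and status.** Section 10.3.1 puts all analyses in the patients who received the product. Section 10.3.2.1 makes the analysis descriptive, without hypothesis tests. Section 10.3 promises a formal SAP before database lock.

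**The concern.** A patient who dies in month 2 cannot have a positive 3-month RCR test, and one who dies in month 10 cannot have a positive 12-month test. If marker status is fixed at time zero, the months a patient had to survive in order to become positive are credited to the marker. This is immortal-time bias, and it favours the positive group even when the marker has no effect.

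The plan leaves room for it. Early deaths stay in the analysis set, so they need some marker value, and none is defined. Long-term or persistent expression is by its nature seen only in patients who live long enough to show it. At stake is the exploratory objective itself: a statement that persistence, or a stronger immune response, goes with longer survival.

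**Working it through.** The plan gives no figure for this analysis to reproduce. Its only calculated design figures, the escalation probabilities in Table 10, do reproduce but have no bearing here.

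**Inputs from the documents.** Median survival of 10 months (GBM with radiation), 12 and 15 months (radiation alone; with temozolomide) and 36 months (anaplastic astrocytoma), all Section 1.1. Follow-up up to 5 years (Section 4.9). 18-36 patients (Section 10.2). Sampling times as above. Radiation starts on Day 10-14 and lasts about six weeks (Section 4.6.2), so the post-radiation sample falls between about Day 10 + 42 + 14 = 66 and Day 14 + 42 + 28 = 84.

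**Assumptions not in the documents.** Exponential survival; a marker with no effect on survival; RCR positivity of 5-30%.

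**Step 1: deaths before each sample.** P(dead by t) = 1 - 2^(-t/median), t in months.

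| Median | Day 28 | 3 mo | 6 mo | 12 mo | 24 mo |
|---|---|---|---|---|---|
| 10 | 6.2% | 18.8% | 34.0% | 56.5% | 81.1% |
| 12 | 5.2% | 15.9% | 29.3% | 50.0% | 75.0% |
| 15 | 4.2% | 12.9% | 24.2% | 42.6% | 67.0% |
| 36 | 1.8% | 5.6% | 10.9% | 20.6% | 37.0% |

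**Step 2: why ever-positive status tracks survival.** With chance q of a positive at each test, a patient who reaches k tests is ever positive with probability 1 - (1 - q)^k. At q = 0.10 this is 0 for a death before 3 months, 1 - 0.9^3 = 27% for a patient who reaches the 12-month test (k = 3), and 1 - 0.9^6 = 47% for one who reaches the 48-month test (k = 6).

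**Step 3: RCR, hazard ratio (HR) under no effect (simulated).**

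- *Ever-positive as a fixed covariate, independent draws at each test.* About 0.58 at q = 5% (15-month median). With 36 patients and medians of 10-36 months: 0.52-0.54 at 10%, 0.43-0.44 at 20%, 0.33-0.36 at 30%. Nominal p < 0.05 occurs in 25-82% of null runs. The plan does no tests, but this is roughly how often the 95% interval would exclude 1.
- *Persistent trait detectable from the 3-month test, earlier deaths coded negative.* About 0.77-0.92.
- *The same trait, patients who die before the test dropped.* About 1.0.
- *Time-dependent covariate.* 0.97-1.03. *6-month landmark.* 0.97-1.09. Nominal p < 0.05 in about 3-7% for both.

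**Step 4: immune response, HR under no effect (simulated).**

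- *Peak value, per SD of a single sample.* About 0.93-0.97 for samples to Day 28; about 0.89-0.98 with a post-radiation sample at about Day 75.
- *Any positive sample, unsampled patients counted negative (medians 10-15 months).* 0.90-0.98 to Day 28, and 0.83-0.97 with samples in week 2-3 and about week 11. Nominal p < 0.05 in 5-8% and 4-8% of runs.
- *Precision, for comparison.* At a 15-month median, the 95% interval around a null HR per SD runs from about 0.70 to 1.44 with 36 patients and from 0.57 to 1.76 with 18.
- *Landmark at the last sample.* 0.96-1.07.

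**The case against.** The largest figures belong to an analysis that the plan does not specify. The Cox sentence covers immune response only. For RCR the documents speak of correlation, name no model, and make even that conditional on a positive finding; with no positives there is nothing to bias. The result also depends on coding: a persistent trait read at the 3-month test, with unsampled patients treated as missing, shows no bias. Likewise, if immune response were read on Day 28 and patients without that sample were omitted, nobody in the analysed set could die before Day 28. The Cox risk sets would then equal those of a Day 28 landmark, and the estimates would be identical. All this stands, and it limits the size of the point. It does not remove it, because the plan commits to none of these codings, and omitting unsampled patients departs from Section 10.3.1 as written.

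A reader might infer that a spurious survival advantage for immune responders is the expected result of the named Cox model. The documents do not support that: mandatory sampling ends on Day 28, the later sample is optional, and the bias is small beside the width of the interval.

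A reader might also infer that the model pools the resectable and unresectable arms. Section 10.3.2.4 does not mention arm, so pooling is not stated. It would in any case be a matter of confounding, not immortal time.

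Finally, the work is exploratory and descriptive, and detail is deferred to a later SAP. That lowers the severity. But a hazard ratio reported without a p-value is still biased, and the promised SAP is where the rule can be fixed before outcomes are examined.

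**Conclusion.** The concern holds in a limited form. The plan relates post-injection markers to survival that starts at or before injection, in all injected patients, with nothing to handle deaths before sampling.

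For RCR and persistent expression the risk is large but conditional on coding: a null hazard ratio of about 0.33-0.58 if ever-positive is a fixed covariate, about 0.77-0.92 for a persistent trait with early deaths coded negative, and about 1.0 for that trait if unsampled patients are dropped. For immune response, the only marker with a named model, the bias is small: about 0.93-0.97 for a peak value to Day 28, and about 0.89-0.98 with the optional post-radiation sample.

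These figures rest on exponential survival, medians of 10-36 months and assumed positivity of 5-30%. Severity is low to moderate, since the MTD is unaffected.

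**What to change.** In the SAP, before database lock:

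- **Immune response.** Define it from samples up to Day 28 and start survival at a Day 28 landmark among patients alive then. Describe the post-radiation sample only. List deaths before Day 28 and state how missing samples in survivors are handled.
- **RCR.** Enter it as a time-dependent covariate that switches on at the date of the first positive sample. If positives are few, only list them. Avoid a 12-month landmark: at a 15-month median it excludes about 43% (0.426 × 18 = 7.7 to 0.426 × 36 = 15.3 patients).
- **Reporting.** Give the hazard ratio with its confidence interval and no test.
- **Consistency.** Reconcile the survival origin (Section 6.2 against 10.3.2.3) and the immune sampling times (Section 9.0 against the Study Summary and Table 4).

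Stratifying by arm is a sensible but separate addition.

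The cost is SAP wording, with no new visits or samples. The Day 28 landmark loses about 4-6% at medians of 10-15 months (0.042 × 18 = 0.8 to 0.062 × 36 = 2.2), or 1-2 patients. The time-dependent model excludes nobody.

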10.3.3 Safety Analyses

Safety endpoints include adverse events (including serious adverse events), deaths, laboratory parameters, vital signs, physical examination and ECG.

All Adverse event will be coded by System Organ Class (SOC) and Preferred Term using Medical Dictionary for Regulatory Activities (MedDRA) dictionary, and will be presented in frequency tables (overall and by intensity [CTCAE grading]) by SOC. In tables showing the overall incidence of adverse events, subjects who experienced the same event on more than one occasion are counted only once in the calculation of the event frequency. Listings will be presented by subject for all adverse events as well as for serious adverse events, adverse events associated with death, and adverse events leading to discontinuation from the study, unanticipated problems involving risks to subject or others. The following information will be included: start date, stop date, severity, relationship, outcome, and duration. Deaths will be listed and summarized descriptively.

Laboratory data will be presented as summary statistics by dose group using both shift and frequency tables. For each continuous laboratory parameter, results will be categorized as low, normal or high based on the laboratory normal ranges. Subjects who had a shift to low and those who had a shift to high from baseline to any post-dosing assessment will be summarized. All out-of-range and clinically significant laboratory results will be identified in subject data listings.

Individual patient values of vital sign parameters including systolic and diastolic blood pressure and heart rate will be listed by patient. The absolute and percentage changes from baseline will be computed and potentially serious changes will be flagged. Appropriate summary statistics will be provided for all vital sign parameters.

The number and percentages of subjects in each dose group with normal and abnormal ECG performance status and physical examination results will be presented for evaluations at baseline and final visit. For each body system, changes in subjects' findings from baseline to final visit (no change, normal to abnormal, or abnormal to normal) will be tabulated for each dose group.

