3.1 Inclusion Criteria

3.1.1 Patients must have a presumed newly identified malignant glioma based on clinical and radiologic evaluation. Pathologic confirmation of malignant glioma must be made at the time of stereotactic biopsy or resection on frozen section by a neuropathologist prior to NSC-CRAd-S-pk7 injection; if this is not possible, the injection will not be performed and the subject will no longer be eligible for the study.

3.1.2 Patients must be planning to undergo standard radiation/chemotherapy.

3.1.3 The tumor must be accessible for injection.

3.1.4 Patients must be age \geq 18 years.

3.1.5 Patients must exhibit a Karnofsky performance status of \geq 70.

3.1.6 Patients must have adequate organ and bone marrow function within 28 days prior to registration, as defined below:

- SGOT (AST) $<$ 3x upper limit of normal

- Serum creatinine $<$ 2mg/dl

- Platelets $>$ 100,000/mm³ and WBC $>$ 3000/mm³

3.1.7 Be able to undergo a brain magnetic resonance imaging scan.

3.1.8 Females of child-bearing potential (FOCBP) and males must agree to use adequate contraception (hormonal or barrier method of birth control; abstinence) prior to study entry, for the duration of study participation, and for 90 days following completion of therapy. Should a female patient become pregnant or suspect she is pregnant while participating in this study, she should inform her treating physician immediately.

NOTE: A FOCBP is *any woman* (regardless of sexual orientation, having undergone a tubal ligation, or remaining celibate by choice) who meets the following criteria:

- Has not* undergone a hysterectomy or bilateral oophorectomy
- Has had* menses at any time in the preceding 12 consecutive months (and therefore has not been naturally postmenopausal for $>$ 12 months)

3.1.9 FOCBP must have a negative pregnancy test within 7-10 days prior to receiving study drug.

3.1.10 Patients must have the ability to understand and the willingness to sign a written informed consent prior to registration on study.

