8.1.10 Side effects

Toxicities Associated with Adenoviral Injection

In previous trials of intratumoral adenoviral injection, toxicity was rare, and overall, the approach has been well tolerated. A summary of grade 3 and 4 toxicities seen in the previous trials is provided in **Table 8** below. In the Phase I study in recurrent brain

tumors, CNS toxicity (lethargy, confusion, grade 3 hyponatremia, fever, leukocytosis, intratumoral hemorrhage in 1, hydrocephalus in the other) was observed in 2/2 patients at 2×10^{12} vp dose level. In the lower dose levels, no DLTs were observed but transient and less severe events included seizure, small intratumoral hemorrhage, worsening of neurologic symptoms, mild hyponatremia. One patient at the highest dose level in the prostate dose escalation study experienced grade 4 transient thrombocytopenia which was considered a DLT and also transient grade 3 elevation in liver transaminases.

Table 8 – Summary of Grade 3 and 4 Toxicities In Trials With Adenovirus		
Patient Characteristics	Treatment Specifics	Toxicity
Recurrent malignant gliomas IND 6371 13 patients Trask et al, 2000	Dose escalation: 2×10^9 vp, (2 pts) 2×10^{10} vp, (2 pts) 2×10^{11} vp, (7 pts) 2×10^{12} vp, (2 pts) Delivery: Stereotactic injection Prodrug: GCV Concurrent tx: none	CNS toxicity in 2/2 patients at 2×10^{12} vp dose level Therapy tolerated by other 11 patients including 7/7 patients treated at 2×10^{11} vp
Recurrent ovarian cancer, stage IIIC IND 7311 10 patients Hasenburg et al, 2001	Dose escalation: 2×10^{10} vp, (2 pts) 2×10^{11} vp, (2 pts) 2×10^{12} vp, (2 pts) 2×10^{13} vp, (4 pts) Delivery: Intraperitoneal Prodrug: ACV or Valacyclovir Concurrent tx: Topotecan	No significant toxicity attributable to gene therapy.
Recurrent prostate cancer IND 6636 18 patients Herman et al, 1999	Dose escalation: 2×10^9 vp, (4 pts) 2×10^{10} vp, (5 pts) 2×10^{11} vp, (4 pts) 2×10^{12} vp, (5 pts) Delivery: Intraprostatic Prodrug: GCV Concurrent tx: none	One patient at 2×10^{12} vp dose level had transient grade 4 thrombocytopenia and grade 3 hepatotoxicity
Recurrent prostate cancer (radiation failures), multiple injections 27 patients (18 new patients plus 9 additional injections in patients from first study) Shalev et al, 2000; Miles et al, 2001	Dose: $2-6 \times 10^{11}$ vp Delivery: Intraprostatic Prodrug: GCV Concurrent tx: none	Grade 3 hypertension in one patient requiring anti-hypertensive therapy

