8.1.10 Side effects

- The most common adverse reactions ($\geq 10\%$ incidence) are: alopecia, fatigue, nausea, vomiting, headache, constipation, anorexia, convulsions, rash, hemiparesis, diarrhea, asthenia, fever, dizziness, coordination abnormal, viral infection, amnesia, and insomnia.
- The most common Grade 3 to 4 hematologic laboratory abnormalities ($\geq 10\%$ incidence) that have developed during treatment with temozolomide are: lymphopenia, thrombocytopenia, neutropenia, and leukopenia. Allergic reactions have also been reported.
- Less likely but severe adverse reactions include myelodysplastic syndrome and hepatotoxicity

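### The laboratory shift table in Section 10.3.3 uses only low/normal/high, so it can miss worsening in subjects already out of range at entry and cannot tell severe changes from trivial ones

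*Combined protocol and SAP*

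**What the plan says.** Section 10.3.3 (Safety Analyses) sets out the laboratory analysis in four steps:

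- Output: "Laboratory data will be presented as summary statistics by dose group using both shift and frequency tables".
- Categories: "For each continuous laboratory parameter, results will be categorized as low, normal or high based on the laboratory normal ranges".
- Counting rule: "Subjects who had a shift to low and those who had a shift to high from baseline to any post-dosing assessment will be summarized".
- Listings: "All out-of-range and clinically significant laboratory results will be identified in subject data listings".

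The counting rule sets no toxicity grade, no minimum size of change and no time window. CTCAE grade appears in the same section only for adverse events, which "will be presented in frequency tables (overall and by intensity [CTCAE grading]) by SOC".

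Section 3.1.6 fixes the baseline range. AST must be below "3x upper limit of normal", creatinine below 2 mg/dl, platelets above 100,000/mm³ and WBC above 3,000/mm³. AST values between 1 and 3 times ULN are therefore eligible.

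The Statistical Considerations part of the Study Summary goes further than 10.3.3: besides shift tables, it plans summaries of laboratory change from baseline over time. Section 10.3 defers further analysis detail to a formal SAP, due before database lock.

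**The concern.** A shift count should show who got worse. This one registers only a crossing of the normal-range limit. A subject already beyond the limit in the harmful direction has no further limit to cross, however far the value moves. A subject just inside it is counted after a negligible change, in the same cell as a subject who falls from normal to Grade 4.

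The analytes affected are ones the protocol itself treats as safety signals. For an earlier adenoviral vector trial in prostate cancer, Section 8.1.10 reports "grade 4 transient thrombocytopenia which was considered a DLT and also transient grade 3 elevation in liver transaminases". The temozolomide part of Section 8 lists, at 10% incidence or more, "The most common Grade 3 to 4 hematologic laboratory abnormalities", and names lymphopenia, thrombocytopenia, neutropenia and leukopenia.

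Timing adds to the problem. Sections 4.1 and 4.6.2 start radiotherapy and temozolomide 10 to 14 days after injection. A count over any post-dosing assessment merges the injection-only window with chemoradiation, and the trial has no control arm to help separate them.

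Cohorts have 3 to 6 subjects per dose and arm (Section 4.2). One subject counted or not counted is 1/6 = 17% to 1/3 = 33% of a row.

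**Working it through.** The plan gives no figure for laboratory shifts, so there is none to reproduce. The Table 10 escalation probabilities do not enter. Two checks apply.

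**1. The rule applied to values that entry allows**

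Inputs: the categories and counting rule from 10.3.3, and the entry limits from 3.1.6. Assumptions, because the documents do not give them: a lower normal limit for platelets of 130,000 to 150,000/mm³; AST Grade 3 above 5 and Grade 4 above 20 times ULN; platelets Grade 3 below 50,000 and Grade 4 below 25,000/mm³.

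| Analyte | Baseline | Post-dose | Category | Counted? | Grade (assumed cut-offs) |
|---|---|---|---|---|---|
| AST, × ULN | 2.9 | 6 | high to high | no | 1 to 3 |
| AST, × ULN | 2.9 | 21 | high to high | no | 1 to 4 |
| AST, × ULN | 1.00 | 1.01 | normal to high | yes | 0 to 1 |
| AST, × ULN | 0.9 | 6 | normal to high | yes | 0 to 3 |
| Platelets | 110,000 | 20,000 | low to low | no | 1 to 4 |
| Platelets | 150,000 (at limit) | 149,000 | normal to low | yes | 0 to 1 |
| Platelets | 200,000 | 20,000 | normal to low | yes | 0 to 4 |

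The AST categories follow from the documents alone, because the entry limit is itself a multiple of ULN. The platelet rows need the laboratory's lower limit to lie above the entry floor; the 110,000 and 200,000 rows give the same result at 130,000, 140,000 and 150,000. The same condition applies to WBC. The cut-offs affect only the last column. If a full three-by-three table is printed, the high-to-high subject sits on the diagonal with subjects who did not change.

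**2. How often the rule counts a shift when nothing has happened**

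Model: standardised value X = √r·U + √(1−r)·E, with U fixed per subject and E new at each test, both standard normal. The normal range is ±1.96 (central 95%) and the baseline value is in range. The quantity is the probability that at least one of k post-dosing values lies beyond the limit in one stated direction, since the rule counts low and high separately. The within-subject correlation r and the number of tests k are assumptions. There were one million simulated subjects for each r, before restricting to in-range baselines.

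| r | k = 6 | k = 8 | k = 12 |
|---|---|---|---|
| 0.5 | 9.4% | 11.5% | 14.9% |
| 0.7 | 6.7% | 8.0% | 10.0% |
| 0.85 | 4.3% | 5.0% | 6.1% |

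For a full cohort of six in-range subjects and 6 to 8 tests, the expected number of false shifts per analyte and direction is 6 × 0.043 = 0.26 to 6 × 0.115 = 0.69.

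**The case against.** The strongest reply is that the shift count is one output among several, and the others do show severity:

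- The Study Summary's change-from-baseline summaries would include a high-to-higher AST. Being over time, they can also separate visits before and after temozolomide starts.
- Section 10.3.2.1 gives minimum and maximum. With 3 to 6 subjects per cell, an extreme value would show as one of these.
- Section 7.2.1 treats an abnormal laboratory finding as a possible adverse event and asks for worsening of pre-existing conditions to be recorded. Adverse events are tabulated by grade.
- Section 4.2.1 brings Grade 3 hematologic and non-hematologic toxicity into the DLT definition.
- All out-of-range results are listed, and out-of-range subjects still appear in the frequency tables.

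Most of this stands. A reader might infer that Grade 3-4 laboratory toxicity would go unreported, or that subjects with abnormal baselines are dropped. The documents support neither.

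Some of it stands only in part. Listings are not summaries. The adverse-event route depends on what the investigator records: Section 7.2.1 asks for the diagnosis rather than the laboratory finding where one is known, and Section 7.2.2 names CTCAE grading only for non-hematologic events, although 4.2.1 and 7.3.2 apply it without that limit. Section 10.3.3 does not repeat the change-from-baseline summaries for laboratory data. No planned laboratory table sets baseline grade against worst grade.

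The pending SAP is a natural place to add such a table. That makes the change easy; it does not remove the need for it.

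**Conclusion.** The point holds for the shift table and goes no further. As written, the table misses worsening in subjects already out of range in the harmful direction, and it puts trivial and severe changes in one cell. For AST this follows from Sections 10.3.3 and 3.1.6 alone. For platelets and WBC it rests on the laboratory's lower limit being above the entry floor.

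Under the stated model, the false-shift chance per analyte and direction is about 4% to 11.5% over 6 to 8 tests and 6% to 15% over 12. Two larger readings are tempting. Adding low and high together roughly doubles these figures, to 9% to 23% and 12% to 30%, but the rule counts the directions separately. Multiplying an assumed share of subjects with abnormal baselines by the arm size would give subjects at risk of being missed, not subjects missed, and the documents give no such share.

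The analysis is descriptive. No test, sample size, DLT or MTD decision uses this table. It should be changed because safety is a primary objective and laboratory parameters are a named safety endpoint, but it does not threaten the trial's main conclusion.

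**What to change.** In Section 10.3.3 and the pending SAP:

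- Tabulate baseline CTCAE v4.03 grade against worst post-injection grade, per analyte and direction, by arm and dose.
- Add the number of subjects who worsen by at least one grade and the number who reach Grade 3-4.
- Show this separately for injection to start of radiotherapy/temozolomide, and from that start onward.
- Keep the low/normal/high table for analytes that have no CTCAE grade.
- Align 10.3.3 with the change-from-baseline summaries in the Study Summary.

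The cost is SAP wording and one programmed table. CTCAE v4.03 is already the grading scale and the samples are already scheduled, so no new data are needed. The downside is slightly more output.
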